11.2.7 Handling of Missing Data

All analyses will be performed only on subjects undergoing surgical procedures during which treatment (HemoStyp or Surgical) is applied to target bleeding sites. There will be no imputation of missing data for any parameters or for early terminated subjects.

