Statistical Analyses:	
Sample Size A non-inferiority comparison will be performed to determine if the hazard ratio with an overall sample size of 212 subjects (106 HemoStyp group and 106 Surgicel group) achieves 80% power at a 0.05 significance level when the hazard ratio is actually 1.33 (median survival is 3.0 minutes for HemoStyp and 4.0 minutes for Surgicel). The non-inferiority ratio is 0.75 (corresponding to margin of 1 minute). It is anticipated that the proportion of subjects observed with the event during the study is 0.90 for the HemoStyp group and 0.92 for the Surgicel group. These results assume that the hazard ratio is constant throughout the study and that Cox proportional hazards regression or the non-inferiority log-rank test is used to analyze the data.
 
It is anticipated that approximately 710 subjects will be screened to randomize approximately 234 subjects with an anticipated drop-out rate of approximately 10%.

Efficacy Analyses

Analysis of Primary Endpoint

The time to hemostasis will be measured from start of study treatment to the achievement of hemostasis at the target bleeding site (TBS), or to the end of the 10-minute observation period. The time to hemostasis will be considered as censored at the end of the 10-minute observation period. Time to hemostasis will be quantified in minutes according to its nominal time point. When re-bleeding occurs, and the cessation of bleeding is again achieved at a later time point, the effective time to hemostasis will be the latter time point. The time to hemostasis will be the time from start of study treatment to that last effective hemostatic time point.

The primary endpoint analyses will be based on Intent-to-Treat (ITT) population. The primary analysis is the test of non-inferiority of HemoStyp compared with Surgical. The primary endpoint will be tested using Cox proportional hazards regression. The primary endpoint will be tested for superiority after the secondary endpoints have been analyzed. The primary endpoint analyses will also be performed on the Per Protocol (PP) population.

Analysis of Secondary Endpoint

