11 STATISTICAL AND ANALYTICAL PLANS

A detailed Statistical Analysis Plan (SAP) will be written and approved prior to database lock. The SAP will describe all planned analyses based on the statistical design of this study and the subsequent data collected. A brief overview of key statistical analyses is provided below.

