11.1 Determination of Sample Size

A non-inferiority comparison will be performed to determine if the hazard ratio with an overall sample size of 212 subjects (106 HemoStyp group and 106 Surgicel group) achieves 80% power at a 0.05 significance level when the hazard ratio is actually 1.33 (median survival is 3.0 minutes for HemoStyp and 4.0 minutes for Surgicel). The non-inferiority ratio is 0.75 (corresponding to margin of 1 minute). It is anticipated that the proportion of subjects observed with the event during the study is 0.90 for the HemoStyp group and 0.92 for the Surgicel group. These results assume that the hazard ratio is constant throughout the study and that Cox proportional hazards regression or the non-inferiority log-rank test is used to analyze the data.

It is anticipated that approximately 710 subjects will be screened to randomize approximately 236 subjects with an anticipated drop-out rate of approximately 10%.

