11.2.2 Analysis Populations

Intent-To-Treat Population (ITT): The ITT population will include all subjects who are randomized to HemoStyp or Surgicel. The efficacy analysis will be performed using the ITT population.

The Per Protocol population (PP): The PP population will include all subjects who are not major protocol violators with regards to inclusion/exclusion criteria, randomization, and have availability of scheduled data for all treatments and efficacy evaluations.

Safety Population: The safety population will include all subjects who are treated with any amount of HemoStyp or Surgicel. Safety analyses will be performed using the safety population and subjects will be analyzed according to the treatment they actually receive.

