11.2.5 Efficacy Analyses

Primary Endpoint

The time to hemostasis will be measured from start of study treatment to the achievement of hemostasis at the target bleeding site (TBS), or to the end of the 10-minute observation period. The time to hemostasis will be considered as censored at the end of the 10-minute observation period. Time to hemostasis will be quantified in minutes according to its nominal time point. When re-bleeding occurs, and the cessation of bleeding is again achieved at a later time point, the effective time to hemostasis will be the latter time point. The time to hemostasis will be the time from start of study treatment to that last effective hemostatic time point.

Secondary Endpoints

- Percentage of subjects achieving hemostasis at the target bleeding site at 2 minutes and at 5 minutes following the start of study treatment;
- Percentage of subjects with intraoperative hemostasis at the target bleeding site;
- Percentage of subjects with intraoperative re-bleeding from the target bleeding site post hemostasis;
- Postoperative re-bleeding from the target bleeding site requiring surgical re-exploration up to 30 days after surgery.

Analysis of the Primary Endpoint

The primary endpoint analyses will be based on ITT population. The primary analysis is the test of non-inferiority of HemoStyp compared with Surgicel. Cox proportional hazards regression or log-rank test will be used for the analysis of non-inferiority.

The null hypothesis for the testing of the primary endpoint is described below:

H0: HemoStyp is inferior or worse than Surgicel by more than 1 minute for median survival (HR<0.8);

H1: HemoStyp is inferior to Surgicel by less than 1 minute for median survival (HemoStyp is not inferior to Surgicel) ($HR > 0.8$);

If the lower bound 95% confidence interval of $HR > 0.8$, we conclude that HemoStyp is not inferior to Surgicel.

The primary endpoint analyses will also be performed on the PP population.

Analyses of Secondary Endpoints

A two-sided z-test with pooled variance will be used to test the difference for each secondary endpoint. The 95% confidence intervals (CIs) for each secondary endpoint in each group (HemoStyp or Surgicel) will be provided.

Secondary endpoints will be assessed at significant level of 0.05 in the order listed below after achievement of a significant result for the primary endpoint:

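### Section 11.2.7 limits every analysis to treated subjects, which contradicts the all-randomised ITT set used for the primary non-inferiority test

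*Combined protocol and SAP*

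**What the plan says.** Section 11.2.2 defines the analysis sets. For ITT: "The ITT population will include all subjects who are randomized to HemoStyp or Surgicel". No treatment condition is attached. A separate treated set exists for safety: "The safety population will include all subjects who are treated with any amount of HemoStyp or Surgicel".

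The primary non-inferiority test is tied to ITT twice. The synopsis says "The primary endpoint analyses will be based on Intent-to-Treat (ITT) population", and Section 11.2.5 says "The primary endpoint analyses will be based on ITT population".

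Section 11.2.7, under missing data, then says: "All analyses will be performed only on subjects undergoing surgical procedures during which treatment (HemoStyp or Surgical) is applied to target bleeding sites". It also rules out imputation.

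The primary endpoint clock depends on treatment: "The time to hemostasis will be measured from start of study treatment to the achievement of hemostasis". The stopwatch starts on application (Sections 7, 7.2 and 8.7), and the only censoring point is the end of the 10-minute observation period.

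Section 11 describes itself as an overview and defers detail: "A detailed Statistical Analysis Plan (SAP) will be written and approved prior to database lock". The text supplied contains nothing that settles which set governs.

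**The concern.** A subject who is randomised but does not receive the product is in the primary analysis under Section 11.2.2 and out of it under Section 11.2.7. Both cannot apply. If the wider sentence wins, the primary test of an open-label trial compares treated subjects only, although randomisation takes place before application and the surgeon can know the arm at that moment. The protection that randomisation gives is then lost for whoever drops out between the two steps. Section 6.4 also allows subjects who withdraw to be replaced, without saying that the replaced subject stays in the analysis.

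What is at stake is the false non-inferiority rate. A treated-only comparison is biased if non-application is related both to the arm and to how quickly the subject would have stopped bleeding.

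**Working it through.** **1. The sets side by side.** ITT is all randomised subjects. The Safety set is all subjects given any amount of product. Section 11.2.7 keeps only subjects in whom product was applied. ITT restricted by Section 11.2.7 therefore has the same members as the Safety set. The two rules differ only for subjects who were randomised and not treated.

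**2. How many.** The documents give no count. Sections 7.2 and 8.7 place randomisation during surgery, after the site has been graded mild or moderate and judged to need an adjunct. The interval before application is short, so the number is probably small. Counts of 1, 3 and 6 below are assumptions.

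**3. Simulation inputs.**
- 118 per arm: 212/0.90 = 236 (Section 11.1), halved.
- 30-second inspections and censoring at 10 minutes (Sections 7.2 and 11.2.5).
- Success if the lower 95% limit of the Cox hazard ratio exceeds 0.80 (Section 11.2.5). Taking the interval as two-sided, the nominal one-sided error is 2.5%.
- Surgicel median 4 minutes (Section 11.1).
- Event proportions: Section 11.1 expects that "the proportion of subjects observed with the event during the study is 0.90 for the HemoStyp group and 0.92 for the Surgicel group". With a hazard ratio of 1.33 and censoring only at 10 minutes, no proportional-hazards model gives both. Exponential times give 1 − 2^(−10/4) = 0.823 for Surgicel and 1 − 2^(−10/3) = 0.901 for HemoStyp. Fixing Surgicel at 0.92 gives HemoStyp 1 − 0.08^1.33 = 0.965. Both are shown: Model A is exponential (82% Surgicel events); Model B is Weibull with shape 1.411 and scale 5.186 (92%).
- 20,000 trials per case, Efron ties. Monte Carlo standard error is about 0.1 point at 2.5% and 0.2 at 10%.

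**4. False non-inferiority at true hazard ratio 0.80, margin 0.80.**

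| Untreated subjects and handling | Number | Model A | Model B |
|---|---|---|---|
| None | 0 | 2.40% | 2.38% |
| HemoStyp only, random, excluded | 3 | 2.67% | 2.48% |
| HemoStyp only, random, excluded | 6 | 2.59% | 2.48% |
| Equal in both arms, any selection, excluded | 3 or 6 per arm | 2.33–2.72% | 2.36–2.93% |
| HemoStyp only, slower half, excluded | 1 | 2.77% | 2.63% |
| HemoStyp only, slower half, excluded | 3 | 3.48% | 3.53% |
| HemoStyp only, slower half, excluded | 6 | 5.19% | 4.67% |
| HemoStyp only, certain failures, excluded | 6 | 10.62% | 16.73% |

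Section 11.1 uses a margin of 0.75. With hazard ratio and margin both 0.75, slower-half exclusion of three or six gives 3.88% or 5.05% (A) and 3.43% or 5.05% (B), so the picture does not depend on the margin.

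**5. How extreme the last row is.** At hazard ratio 0.80 the expected HemoStyp failures at 10 minutes are 118 × 0.177^0.8 ≈ 29 (A) and 118 × 0.08^0.8 ≈ 16 (B). Excluding six of them removes about 20% or 38% of all failures in that arm. They would have to be recognised before the product was applied.

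**6. The replacement rule.** Once the sentence is narrowed, an untreated subject needs a time and a status. Counting such subjects as non-events at 10 minutes, chosen at random:

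| Untreated | Number | Model A | Model B |
|---|---|---|---|
| Both arms | 3 / 6 per arm | 2.45% / 2.49% | 2.38% / 2.26% |
| HemoStyp only | 3 / 6 | 1.09% / 0.37% | 0.67% / 0.19% |
| Surgicel only | 3 / 6 | 5.37% / 9.95% | 6.64% / 15.08% |
| Surgicel only, excluded instead | 3 / 6 | 2.57% / 2.28% | 2.48% / 2.36% |

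The non-event rule is safe when the untreated are HemoStyp or balanced, and favours HemoStyp when they are mostly Surgicel. If both analyses must succeed, the error cannot exceed the smaller of the two. For six random Surgicel-only subjects that is at most 2.28% (A) or 2.36% (B).

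**The case against.** Four points deserve weight.

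*The sentence may only be meant to remove screen failures.* About 710 subjects are to be screened, and consented patients without a qualifying bleed enter the database (Section 6.3). Separating them from the roughly 236 randomised is a plausible purpose. But those patients are never randomised, so they are already outside ITT, and the sentence turns on treatment applied. This reading softens the conflict and does not remove it.

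*The plan does have a rule for untreated subjects.* This is correct. A reader might infer that it leaves them undefined. As written it excludes them. The absence of a time zero arises only once the sentence is narrowed, which is why the replacement rule belongs in the same edit.

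*A later SAP can settle it.* It can. Approval before database lock is a latest date, and the synopsis gives only the timing of the interim analysis (118 subjects past the 30-day visit), not who sees the results. A reader might infer that the choice will be made with outcomes in view. That is possible in an open-label trial, but the documents do not show it.

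*The large error rates are implausible.* This also stands. A subject who is treated and then fails remains in the analysis. The 10.6% and 16.7% figures need surgeons to identify certain failures before application, in one arm only.

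**Conclusion.** The contradiction between Section 11.2.7 and Sections 11.2.2 and 11.2.5 is plain on the text, and following Section 11.2.7 literally would replace the ITT primary test with a treated-only one.

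Its likely effect is modest. Random or balanced exclusion does no material harm. Exclusion related to arm and prognosis takes the error from 2.4% to about 3.5% with three HemoStyp subjects and about 5% with six. These are illustrations on assumed counts under proportional hazards, not bounds or predictions. The documents do not support reading the certain-failure figures as an expected inflation; they are an extreme case only.

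Severity is minor to should-fix: the number affected is probably small, but the conflict concerns the primary analysis set and is cheap to remove.

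**What to change.** 1. Limit the first sentence of Section 11.2.7 to the Safety population and a named treated-only sensitivity analysis.
2. State in Section 11.2.5 that the primary analysis keeps every randomised subject in the assigned arm, including any later replaced under Section 6.4.
3. In the same edit, and before outcome or interim data are seen, state that randomised-but-untreated subjects enter the primary analysis as non-events censored at 10 minutes in both arms. Claim non-inferiority only if the treated-only analysis agrees.
4. Add randomised-not-treated subjects, by arm and with reasons, to the disposition table in Section 11.2.3. This matters because no rule covers every pattern: if untreated Surgicel subjects would have stopped bleeding quickly, both analyses lean towards HemoStyp.

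The cost is wording, a little extra analysis and some power. At hazard ratio 1.33 and margin 0.80, power with nobody untreated is 95.1% (A) and 96.6% (B). With six per arm counted as non-events it is 93.9% and 94.8%, a loss of under 2 points. If all the untreated are HemoStyp, three give 88.8% and 88.5%, and six give 76.8% and 71.8%. These figures are for the non-event analysis alone. Requiring agreement can only lower power further. That step was not quantified, but it should be slight when few subjects are untreated, since the two analyses then share nearly all their data.

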12 RISK AND BENEFITS OF STUDY

HemoStyp is a patented bioabsorbable hemostatic gauze made from ORC. HemoStyp gauze is applied dry swells slightly as it absorbs blood and rapidly converts into a gel that plugs the wound, eventually dissolving into glucose and saline. There are no known side effects of HemoStyp.

This study may or may not provide any benefits to the patient. However, HemoStyp hemostatic gauze is designed as an adjunct for management of secondary hemostasis in the operative setting and has recently obtained CE mark approval in the EEA.

13 ETHICAL AND REGULATORY CONSIDERATIONS

13.1 Informed Consent

Informed consent will be obtained in accordance with the Declaration of Helsinki, International Conference on Harmonisation (ICH) Good Clinical Practice (GCP), US Code of Federal Regulations for Protection of Human Subjects (21 CFR 50.25(a)(b), CFR 50.27, 45 CFR 46.116(a)(b), and CFR Part 56(a)), the Health Insurance Portability and Accountability Act (HIPAA, if applicable), and local regulations.

The Sponsor-Investigator will prepare the ICF and HIPAA authorization and provide the documents to IRB for approval. The written consent document will embody the elements of informed consent as described in the ICH and will also comply with local regulations. The Sponsor-Investigator will retain an IRB-approved copy of the ICF in the study master file.

A properly executed, written, informed consent will be obtained from each subject prior to entering the subject into the trial. Information should be given in both oral and written form and subjects (or their legal representatives) must be given ample opportunity to inquire about details of the study. If a subject is unable to sign the ICF and the HIPAA authorization, a legal representative may sign for the subject. A copy of the signed consent form will be given to the subject or legal representative of the subject and the original will be maintained with the subject's records.

13.2 Independent Ethics Committee (IEC) or Institutional Review Board (IRB)

The protocol and consent form will be reviewed and approved by the IRB of each participating center prior to study initiation. Unanticipated adverse device effects will be reported to the IRB in accordance with the standard operating procedures and policies of the IRB, and the Investigator will keep the IRB informed as to the progress of the study. The Investigator will obtain assurance of IRB compliance with regulations.

Any documents that the IRB may need to fulfill its responsibilities (such as protocol, protocol amendments, Investigator's Brochure, consent forms, information concerning patient recruitment, payment or compensation procedures, or other pertinent information) will be submitted to the IRB. The IRB's written unconditional approval of the study protocol and the ICF will be in the possession of the Investigator before the study is initiated. The IRB's unconditional approval statement will be transmitted by the Investigator to the Sponsor or designee prior to the shipment of study supplies to the site. This approval must refer to the study by exact protocol title and number and should identify the documents reviewed and the date of review.

Protocol and/or informed consent modifications or changes may not be initiated without prior written IRB approval except when necessary to eliminate immediate hazards to the subjects or when the change(s) involves only logistical or administrative aspects of the study. Such modifications will be submitted to the IRB and written verification that the modification was submitted and subsequently approved should be obtained.

The IRB must be informed of revisions to other documents originally submitted for review; new information that may affect adversely the safety of the subjects of the conduct of the study; an annual update and/or request for re-approval; and when the study has been completed.

13.3 Ethical Conduct of the Study

The study will be conducted in compliance with the ICH Guideline on GCP.

14 ADMINISTRATIVE CONSIDERATIONS

14.1 Modifications to the Protocol

No modifications to the protocol should be made without the approval of both the Principal Investigator and United Health Products. Changes that significantly affect the safety of the subjects, the scope of the investigation, or the scientific quality of the study (i.e., efficacy assessments) will require IRB/IEC notification prior to implementation, except where the modification is necessary to eliminate an apparent immediate hazard to human subjects. United Health Products will submit all protocol modifications to the Food and Drug Administration (FDA).

When circumstances require an immediate departure from procedures set forth in the protocol, the Investigator will contact United Health Products to discuss the planned course of action. If possible, contact should be made prior to the implementation of any changes. Any departures from protocol must be fully documented in the source documentation and in a protocol deviation log.

14.2 Case Report Form Completion

An eCRF will be used to enter all appropriate subject data gathered during the study.

14.3 Access to Records

The Investigator must make the office and/or hospital records of subjects enrolled in this study available for inspection by United Health Products or its representative at the time of each monitoring visit. The records must also be available for inspection, verification and copying, as required by regulations, by officials of the regulatory health authorities (FDA and others). The Investigator must comply with applicable privacy and security laws for use and disclosure of information related to this research set forth in this protocol.

14.4 Subject Privacy

To maintain subject confidentiality, all eCRFs, study reports, and communications relating to the study will identify subjects by initials and assigned subject numbers. As required by federal regulations, the Investigator will allow United Health Products and/or its representatives access to all pertinent medical records in order to allow for the verification of data gathered in the eCRFs and for the review of the data collection process. The FDA (or other regulatory authority) may also request access to all study records, including source documentation for inspection.

As applicable, in accordance with HIPAA and associated privacy regulations, a subject authorization to use personally identifiable health information may be required from each subject prior to research activities. This authorization document must clearly specify what parties will have access to a subject's personal health information, for what purpose and for how long.

14.5 Record Maintenance and Retention

The sponsor-investigator will maintain records in accordance with 21 CFR 812, Subpart G, to include:

- FDA correspondence related to the IDE application and Investigational Plan; including copies of submitted Form FDA 3500A, supplemental IDE applications, current investigator lists, progress reports, notice of device recall or disposition, and failure to obtain informed consent reports
- IRB correspondence (including approval notifications) related to the clinical protocol; including copies of adverse event reports and annual or interim reports
- Current and past versions of the IRB-approved clinical protocol and corresponding IRB-approved consent form(s) and, if applicable, subject recruitment advertisements
- Signed Investigator's Agreements and Certifications of Financial Interests of Clinical Investigators
- Curriculum vitae (sponsor-investigator and clinical protocol sub-investigators)
- Certificates of required training (e.g., human subject protections, Good Clinical Practice, etc.) for sponsor-investigator and listed sub-investigators
- Normal value(s)/range(s) for medical/laboratory/technical procedures or tests included in the clinical protocol
- Laboratory certification information
- Instructions for on-site preparation and handling of the investigational device and/or study treatment or diagnostic product(s), and other study-related materials (i.e., if not addressed in the clinical protocol)
- Decoding procedures for blinded trials (incorporate only if applicable)
- Master randomization list (incorporate only if applicable)
- Signed ICF
- Completed Case Report Forms, signed and dated by sponsor-investigator
- Source Documents or certified copies of Source Documents
- Monitoring visit reports
- Copies of sponsor-investigator correspondence to sub-investigators, including notifications of adverse effect information
- Subject screening and enrollment logs
- Subject identification code list
- Investigational device accountability records, including documentation of device disposal
- Retained biological specimen log (incorporate only if applicable)

- Interim data analysis report(s) (incorporate only if applicable)
- Final clinical study report.

The sponsor-investigator will retain the specified records and reports for up to two years after the marketing application is approved for the investigational device; or, if a marketing application is not submitted or approved for the investigational device, until two years after investigations under the IDE have been discontinued and the FDA so notified.

